#### 11.1.2 Transition from Phase I to Phase II

The DSMB will review all data through Visit 5 (Week 4) for the first three subjects in each arm of

CONFIDENTIAL Page 49 of 75

RDEB Phase I/II Protocol

Final Version 8.0, 29 Oct 2019

Phase I of the protocol and make a recommendation as to whether: 1) treatment of adult (≥ 18 years old) patients in Phase II of the protocol should continue; and 2) the study should proceed with enrollment and treatment of children in Phase II of the protocol. The DSMB will consider cumulative safety data, including adverse events, pertinent laboratory and clinical data in making its recommendation to proceed with treatment of adult subjects in Phase II of the protocol. In addition, the DSMB will also consider evidence of direct benefit (see Section 10.1.2.1) in making its recommendation to proceed with for enrollment of pediatric (aged 7 to 17 years old) subjects in Phase II. Adult subjects will be allowed treatment in Phase II of the protocol upon obtaining the DSMB recommendation to proceed with their treatment. Pediatric patients will only be allowed to enroll into Phase II of the protocol if the DSMB recommends proceeding with enrollment of pediatric subjects into Phase II of the protocol and the FDA provides approval for proceeding to pediatric subjects.

#### 11.1.2.1 Criteria for the Evidence of Benefit

Evidence of benefit is defined as having any one or more of the following three criteria in a single FCX-007 treated wound:

- An increased presence of C7, defined as an increase of 1 or more, relative to baseline, on a biopsy evaluated by immunofluorescence (IF), as measured by a qualified reader.
- The presence of mature anchoring fibrils as designated by a qualified reader.
- Increase in wound healing based on investigator assessment relative to baseline (Day 0) in any wound administered FCX-007.

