# 3 Experimental Plan

### 3.1 Study Design

This is a Phase I/II Study of FCX-007 (Genetically-Modified Autologous Human Dermal Fibroblasts) for Recessive Dystrophic Epidermolysis Bullosa (RDEB) being conducted by Fibrocell to evaluate FCX-007 in subjects with RDEB. Up to twelve subjects will be enrolled, up to six (6) in Phase I, and up to six (6) in Phase II. Phase I will enroll adult subjects only; Phase II can enroll adults and pediatric subjects (aged seven (7) or older). Within Phase I, subjects will be assigned to one of two arms: subjects with NC1+ status will be enrolled into Arm A and subjects with NC1- status will be enrolled into Arm B. The arms will enroll independently. In Phase I, the study may enroll an equivalent number of subjects to Arm A and Arm B (n=3 each arm). In Phase II, the study will target enrolling 3 subjects to each arm, but will allow a disproportionate distribution of subjects between Arm A and Arm B to equal 6 total subjects.

Figure 2 - High-Level Study Design

One administration of FCX-007 will consist of up to sixty (60) 0.25 mL intradermal injections in wounded and/or intact skin. The majority of the injections will be administered around the margin of target wounds and at least 6 injections will be administered to intact skin. The Investigator will attempt to administer all 15mL of FCX-007. This will be accomplished by selecting target wounds that are as close as possible to 54 linear cm, leaving at least 6 administrations for intact skin, for a total of 60 injections.

For the wound administrations, subjects will receive FCX-007 administered intradermally to one, two or three paired target wounds at Visit 3 (Day 0). Subjects will receive a second administration to wounded and/or intact skin at Visit 5 (Week 4).

In this study, one wound in each target wound pair will be used as a control for efficacy and safety evaluations. FCX-007 administered wounds will be compared within paired target wounds to untreated wounds.

CONFIDENTIAL Page 17 of 75

Final Version 8.0, 29 Oct 2019

As there is no previous human experience with FCX-007, treatment administration will be staggered in two places:

- 1. Between the first and second enrolled subjects in each arm.
- 2. Between the third and fourth enrolled subjects in each arm.

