Proceeding to administration of FCX-007 after a stagger requires that the previous subject complete Week 4 evaluations and the Investigator must have received approval from the Data Safety Monitoring Board (DSMB) to continue the study prior to the next subject's FCX-007 administration.

At a minimum, FDA and DSMB approvals are required for enrollment of pediatric subjects. Local oversight committees may also require approval.

Each phase of the study is divided into four (4) periods: Screening, Wound Monitoring, Treatment, and Long-Term Follow-Up. The Screening Period consists of entry criteria evaluations, the collection of one set of three 3-4 mm biopsies for FCX-007 manufacturing, and the identification and photography of potential target wounds. FCX-007 manufacturing requires about 4 months. This period is the Wound Monitoring Period. Subject target wounds may be imaged a minimum of two times (at least 4 weeks apart) during this period. The purpose of the imaging is to identify wounds with the most consistent wound areas that meet criteria, and to establish a baseline area that takes into account natural wound area variation. The Wound Monitoring Period is expected to have a duration of approximately four months; however, this period can extend beyond four months to accommodate patient scheduling, variations in manufacturing duration and protocol mandated delays (i.e. pauses due to staggered treatment).

After FCX-007 manufacturing is complete, Fibrocell (the Sponsor) and the Investigator will mutually agree on the date of receipt of FCX-007. The duration of the Treatment Period may fluctuate between two and four days. The Treatment Period visits (Day -2 to Day 2) will be scheduled so that the day of dosing (Day 0) is the day of receipt of FCX-007. Prior to dosing, wounds are identified that meet treatment criteria based on imaging results obtained. Up to three pairs of target wounds may be identified for each subject and the Investigator will pair the target wounds according to similarity in wound area.

One wound in each pair will receive FCX-007 and the other wound no treatment.

Safety and proof of mechanism evaluations are conducted during site visits at Visits 5, 6, 8 and 10 (weeks 4, 12, 25, 52), and unscheduled visits. Proof of mechanism will be monitored through assays conducted on biopsies taken from target wounds and areas of intact skin in which FCX-007 was administered.

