## 11.1 Data Safety Monitoring Board

A DSMB comprised of the Medical Monitor, enrolling Pls, and Sponsor representatives and/or designee(s) will hold periodic teleconferences to evaluate the safety and treatment status of all subjects available during the study at these stages:

- After the first subject, prior to the treatment of a second subject in each arm
- After Visit 5 (Week 4) for the third subject, prior to treatment of the first Phase II subject, to make a recommendation as to whether: 1) treatment of adult patients in Phase II of the protocol should continue; and 2) the study should proceed with the enrollment and treatment of children in Phase II of the protocol.
- At any other time as needed

The DSMB has the authority to recommend dose or regimen modifications for safety concerns.

A written summary documenting the results and recommendations of each review will be provided to the investigator(s) and maintained on file with the Sponsor. Additional sub-investigators and scientific personnel may participate in reviews, as appropriate.

The DSMB will provide recommendations about stopping or continuing the trial. To contribute to enhancing the integrity of the trial, the DSMB may also formulate recommendations relating to the selection/recruitment/retention of participants, their management, improving adherence to protocol-specified regimens and retention of participants, and the procedures for data management and quality control.

A DSMB charter will dictate procedures, responsibilities, membership, data requirements and meeting timing.

CONFIDENTIAL Page 48 of 75

Final Version 8.0, 29 Oct 2019

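### Criterion 3 of the evidence-of-benefit definition counts any improvement from Day 0 in one treated wound and ignores the randomised untreated wound of the same pair

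*Combined protocol and SAP*

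**What the plan says.** Section 11.1.2.1 sets the rule: "Evidence of benefit is defined as having any one or more of the following three criteria in a single FCX-007 treated wound". The third criterion is "Increase in wound healing based on investigator assessment relative to baseline (Day 0) in any wound administered FCX-007". It gives no minimum size of improvement and no number of wounds or subjects, and it does not mention the control wound.

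Section 11.1.2 says how the definition is used. "The DSMB will review all data through Visit 5 (Week 4) for the first three subjects in each arm" of Phase I, and for children "the DSMB will also consider evidence of direct benefit (see Section 10.1.2.1) in making its recommendation". The section cited there does not exist; the criteria stand in 11.1.2.1. Paediatric entry also requires that "the FDA provides approval for proceeding to pediatric subjects". Section 11.1 adds: "A DSMB charter will dictate procedures, responsibilities, membership, data requirements and meeting timing".

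The rest of the design is built on pairs. Section 3.1 states that "FCX-007 administered wounds will be compared within paired target wounds to untreated wounds", and Section 9.2 assigns the two wounds of a pair at random. Section 9.3.1 has the investigator rate both wounds on eight categories from 0% to 100% healed, and Section 7.3.4 and Table 2 schedule that rating at Visit 5 (Week 4). Table 2 has no rating at Day 0, and the text does not say that the Day 0 image counts as 0% healed.

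**The concern.** Wounds in this disease change without treatment, and the protocol knows it. Section 3.1 gives one purpose of pre-treatment imaging as "to establish a baseline area that takes into account natural wound area variation". Section 5.2 places no restriction on concomitant therapy or skin care, and Section 9.1.1 allows debridement. Any of these can move a treated wound from 0% to the 1-9% category or above by Week 4, and on the text as written that is enough for criterion 3.

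The untreated wound of the pair is the trial's means of separating such change from a product effect. Its score exists at the same visit, but the definition does not use it. A treated wound that healed less than its control still counts as benefit. The label then goes into the recommendation on whether children aged 7 to 17 may be enrolled, so it should mean what it says.

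**Working it through.** **No plan figure to reproduce.** Section 14.1 reports no sample size calculation, and the benefit definition carries no stated error rate. The check asks how often criterion 3 would be met if the product did nothing.

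**Inputs**
- Subjects at the review: 6 (Section 11.1.2, three in each arm) or 3 (Section 11.1 speaks of the third subject only).
- Treated wounds per subject: 1 to 3 (Section 3.1). One pair per subject is used here.
- p, the chance that a wound is rated improved at Week 4 with no drug effect: not in the documents, so assumed over 0.05 to 0.3. It may be low, because Section 9.1 prefers the most stable wounds when several pairs qualify.
- Wounds independent, each either improved or not.

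**Formulas, no drug effect, n subjects**
- A, current rule: 1 - (1 - p)^n.
- B, treated wound must beat its own control, any one pair still enough: in one pair, treated is higher with probability d = p(1 - p), so 1 - (1 - d)^n.
- C, pairing plus a summary (more subjects with treated higher than lower): higher d, lower d, tied 1 - 2d. By symmetry C = [1 - P(equal numbers higher and lower)]/2.

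**Worked case, n = 6, p = 0.3**
- A = 1 - 0.7^6 = 0.882.
- d = 0.3 × 0.7 = 0.21, so B = 1 - 0.79^6 = 0.757.
- Tie probability 0.58. P(equal numbers) = 0.58^6 + 30(0.21²)(0.58^4) + 90(0.21^4)(0.58²) + 20(0.21^6) = 0.038 + 0.150 + 0.059 + 0.002 = 0.248 before rounding of the terms. C = (1 - 0.248)/2 = 0.376.

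| p (assumed) | A, n=6 | B, n=6 | C, n=6 | A, n=3 | B, n=3 | C, n=3 |
|---|---|---|---|---|---|---|
| 0.05 | 0.265 | 0.253 | 0.202 | 0.143 | 0.136 | 0.123 |
| 0.1 | 0.469 | 0.432 | 0.291 | 0.271 | 0.246 | 0.204 |
| 0.2 | 0.738 | 0.649 | 0.355 | 0.488 | 0.407 | 0.291 |
| 0.3 | 0.882 | 0.757 | 0.376 | 0.657 | 0.507 | 0.326 |

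**Separating the two changes.** At p = 0.3 and n = 6, pairing alone removes 0.882 - 0.757 = 0.125, and the summary over subjects removes a further 0.757 - 0.376 = 0.381.

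**Two results that do not depend on p**
- B is never easier to meet than A. A treated wound in a higher category than its control must itself be above 0%.
- Under C, random assignment makes more-higher and more-lower equally likely when there is no effect. Neither can exceed 0.5, provided the rating is unbiased. Rule A tends to 1 as p or the number of wounds grows.

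**Cost when the product works.** Let q be the chance that treated is higher given no tie, assumed 0.7. Rule C passes in 74% (no ties) or 73% (30% ties) with 6 subjects, and in 78% or 62% with 3. Rule B is far easier to meet: with 3 pairs and 30% ties, treated is higher with probability 0.7 × 0.7 = 0.49 per pair, so 1 - 0.51^3 = 0.867.

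**The case against.** The strongest reply is that the definition decides nothing alone. The DSMB considers benefit alongside all data through Week 4, and those data include the control wounds' ratings. FDA approval is required, local committees may add their own requirement (Section 3.1), and the charter may already say how benefit is to be read. All of this stands and limits the consequence. A reader might infer that one lucky wound opens the trial to children, or that the decision is made without sight of the controls; the documents support neither.

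A second reply is that pairing does little by itself. This also stands. It would be tempting to credit the fall from 0.882 to 0.376 to the control comparison, but most of it comes from no longer letting one wound decide. An unpaired majority, at least 4 of 6 treated wounds improved, would pass with no effect in only 0.070 at p = 0.3. That rule has no ceiling, however: at p = 0.7 it passes in 15(0.7^4)(0.3²) + 6(0.7^5)(0.3) + 0.7^6 = 0.744, while C stays at 0.376, since p(1 - p) is again 0.21.

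Third, a summary across subjects does not fit the single-wound condition in the opening line of 11.1.2.1, and any threshold is a trade-off on which people may differ. This is right, so no threshold is proposed below.

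Finally, a pilot with exploratory analyses (Section 14.2) need not control error rates. That is true, but it does not explain why the definition ignores a control that is already measured.

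**Conclusion.** The point holds in a limited form and should be fixed. Criterion 3 can label natural healing as direct benefit even when the untreated pair healed as much or more, although the control's rating is available at the same visit. That conclusion comes from the text and does not depend on p.

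The size does depend on p, which is assumed. With six subjects and one pair each, the current criterion is met with no drug effect in 0.265 of cases at p = 0.05 and 0.882 at p = 0.3. Pairing alone gives 0.253 and 0.757; pairing with the summary gives 0.202 and 0.376. The probability gain is small if wounds are stable. What pairing itself contributes is that a wound which does not outperform its control no longer counts and, with the summary rule, that the chance of passing under no effect cannot exceed 50%, given random assignment and unbiased rating.

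Two weaknesses would remain. The investigator assigns and rates the wounds with no blinding described, and pairing does not remove rater bias. Criteria 1 and 2 also lack a control comparison, and either can still satisfy the definition.

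**What to change.** - Restate criterion 3 in Section 11.1.2.1: the treated wound is in a higher healing category than its untreated pair at the review visit. Ties do not count, and the Day 0 image is the 0% reference.
- Give the DSMB the tally of treated higher, tied and lower over all reviewed pairs and subjects, so that one favourable pair is read in context. Leave any numerical threshold to the sponsor and the DSMB charter.
- If criterion 3 is to be judged on the tally, amend the opening line of 11.1.2.1 so that its single-wound condition applies to criteria 1 and 2 only.
- State that rating is unblinded and that criteria 1 and 2 have no control comparison.

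The cost is wording in 11.1.2, 11.1.2.1 and the charter. Both wounds are already rated at Week 4. The downside is a criterion that is harder to meet when the product works: judged on the summary rule at q = 0.7, it would fail in roughly 22% to 38% of cases with 3 or 6 subjects, which could delay paediatric enrolment.

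Separate editorial items: correct the cross-reference in 11.1.2, and reconcile Table 2 with Sections 7.3.2, 7.3.4, 9.4.1, 10.1, 10.2.1 and 10.2.2, which differ on biopsies at Day 0 and Week 4.

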## 11.2 Medical and Medication History

The Investigator or delegated staff performs a complete medical history at Screening, including a medication history. The Investigator or staff must record all clinically or medically relevant information. Medical and medication history are reviewed and updated at visit 2 and visit 3.

Select medical history is also reviewed during Prescreening per the process outlined in Section **7.1.1 (Prescreening)** above. The medical history will include respiratory, cardiovascular, renal, gastrointestinal, hepatic, endocrine, hematological, neurological, psychiatric and other diseases.

CONFIDENTIAL Page 50 of 75

Fibrocell Technologies RDEB Phase I/II Protocol

Final Version 8.0, 29 Oct 2019

## 11.3 Physical Examination

A qualified individual will perform a full physical examination Visit 1, 3, and Visit 10. Body systems evaluated will include:

- General appearance
- HEENT (Head, Ears, Eyes, Nose, Throat)
- Spine/Neck/Thyroid
- Respiratory
- Cardiovascular
- Abdomen
- Nervous System
- Musculoskeletal

Abnormalities or changes in severity noted during the exam should be reported in the source document and on the appropriate CRF page. If a new clinically relevant finding occurs (not noted prior to FCX-007 administration), an adverse event form must be completed. In addition, resolution of any abnormal findings during the study will be noted in the source document and appropriate CRF if clinically significant.

#### 11.4 Skin Examination

A qualified individual will perform a skin examination at all visits to the Investigative Site. If at any point in the study a skin cancer occurs in the region of the FCX-007 administration, attempts will be made to collect samples of the skin cancer to evaluate cells for the presence of viral vector.

## 11.5 Vital Signs

Vital sign measurements include systolic and diastolic blood pressure, pulse, and respiratory rate as well as temperature. Blood pressure, pulse, and respiratory rate are taken after subjects are in a rested state. Blood pressure determined by cuff (manual or automated) is acceptable although the same method should be used throughout the study. Temperature, oral or tympanic, is acceptable although the same method should be used throughout the study.

CONFIDENTIAL Page 51 of 75

Fibrocell Technologies RDEB Phase I/II Protocol Final Version 8.0, 29 Oct 2019

## 11.6 Laboratory Evaluations

#### 11.6.1 Serum Chemistry and Hematology

Whenever possible, the amount of blood collected should be minimized. Serum chemistry and hematology laboratory analyses will occur locally. Reference ranges will be supplied by the laboratory and used to assess the laboratory data for clinical significance and out-of-range pathological changes. Abnormal laboratory values which are unexpected or not explained by the subject's clinical condition should be repeated until confirmed, explained or resolved. Changes from the Day -2 lab results will be recorded as an AE if deemed clinically relevant by the Investigator or medically qualified designee. The following evaluations will be conducted:

#### Serum Chemistry / Metabolic Panel

- Albumin	
 
AST (SGOT)
 
	
 
Bilirubin, direct & indirect
 
	- Globulin
- Alkaline Phosphatase Total	- Urea Nitrogen	- CO2	- Potassium
- Anion Gap	- Calcium	- Creatinine	- Sodium
- ALT (SGPT)	- Chloride	- Glucose	- Total Bilirubin
,			- Total Protein

#### Hematology / Complete Blood Count with Differential

- WBC	
 
Platelet Count
 
	- MCHC	
 
Monocytes, % and abs
 

- Hemoglobin	- MCV RDW	
 
Neutrophils, % and abs
 
	- Eosinophils, % and abs

 
Hematocrit
 
	- RBC MCH	- Lymphocytes, % and abs	- Basophils, % and abs

#### 11.6.2 Urine Pregnancy Test

A urine pregnancy test will be performed at the Visit 1 and Visit 2 for women of childbearing potential.

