### 4.2 Exclusion Criteria

Subjects will be excluded from the study if any of the following criteria are met:

- 1. Medical instability limiting ability to travel to the investigative center.
- 2. Active infection with HIV, hepatitis B or hepatitis C, as determined by hepatitis B surface antigen screening, detection of hepatitis C antibodies, or positive result of hepatitis C PCR analysis.
- 3. The presence of antibodies to the basement membrane of monkey esophagus by indirect immunofluorescence using the subject's serum.
- Evidence of systemic infection.
- 5. Current evidence of metastatic squamous cell carcinoma at the site to be injected.
- 6. Known allergy to any of the constituents of the product.
- 7. Active drug or alcohol addiction.
- 8. Hypersensitivity to anesthesia chosen (lidocaine/prilocaine cream, moderate sedation, or general anesthesia).
- 9. Receipt of a chemical or biological study product for the specific treatment of RDEB in the past six months
- 10. Women who are pregnant or breast-feeding.
- 11. Any clinically significant abnormal laboratory result from Day -2 (Grade 2 or higher on the National Cancer Institute [NCI] toxicity scale), except for the following:
  - a. Albumin < 2.5 g/dL,
  - b. Leukocytes > 20K/uL,
  - c. Hemoglobin < 7.5 g/dL
- 12. Clinically significant abnormalities (Grade 2 or higher on the NCI toxicity scale) identified through medical history and physical examination at Day 0, with the following exceptions:
  - a. Anorexia, can enroll up to Grade 4 (inclusive)
  - b. Constipation, can enroll up to Grade 2 (inclusive)
  - c. Dysphagia, can enroll up to Grade 4 (inclusive)
  - d. Keratitis, can enroll up to Grade 4 (inclusive)
  - e. Bone pain, can enroll up to Grade 2 (inclusive)

CONFIDENTIAL Page 21 of 75

Final Version 8.0, 29 Oct 2019

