# 5.3 Withdrawal of Subjects

A subject is free to withdraw from the study at any time for any reason without prejudice to their future medical care by the physician or at the institution. The Investigator or Sponsor may also withdraw the subject at any time in the interest of subject safety or for other reasons. Criteria for withdrawal include:

- 1. Consent/assent is withdrawn
- 2. The subject refuses treatment and/or procedures/observations.
- 3. Occurrence of unmanageable adverse events, or pregnancy.
- 4. For other reasons (e.g., significant protocol violation, non-compliance).
- 5. The Sponsor may be contacted if clarification is required.

The primary reason for withdrawal must be recorded on the CRF. Comments or complaints made by the subject must also be recorded on the CRF. Withdrawal information will be communicated to the DSMB at each meeting. Withdrawal should be discussed with the medical monitor prior to withdrawal when possible. Subjects who wish to discontinue treatment or study procedures after receipt of FCX-007 will be asked to continue in the Long-Term Follow-Up Period (Section **7.5**). Subjects who withdraw prior to FCX-007 administration will be considered a screen failure and will be replaced. The Sponsor reserves the right to terminate the study.

CONFIDENTIAL Page 22 of 75

[figure not shown]
Final Version 8.0, 29 Oct 2019

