# 6.2 Labeling, Packaging, Storage and Handling

### 6.2.1 Packaging and Labeling

### 6.2.1.1 Packaging

Investigational product will be provided to the Investigative Site as an opaque cell suspension in 2.0 mL cryovials containing approximately 1.2 mL of FCX-007 per vial with a recoverable volume of 1.0 mL per vial.

Up to thirty (30) vials of FCX-007 will be provided per subject; 15 vials for Day 0, and 15 vials for week 4.

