### **Time Frame Between Subjects**

The second subject in each arm will not be treated until after the first subject has completed the 4-week evaluation. The DSMB will meet after the first subject has completed visit 5 (Week 4) to review data and determine whether the second subject in each arm can be treated. Likewise, the fourth subject (and first potential pediatric subject) in each arm will not be treated until after the third subject has completed the 4-week evaluation and the DSMB has reviewed the data. DSMB and FDA approval will be required prior to enrollment of any pediatric subject.

CONFIDENTIAL Page 25 of 75

FI-EB-001

Fibrocell Technologies

RDEB Phase I/II Protocol

Final Version 8.0, 29 Oct 2019

Table 2 - Schedule of Events

				Trea	tment F	Period							
Event	Pre- screen	Visit 1 Screen¹	Wound Monitoring Period 	V2 Day -2 	V3 Day 0	V4 Day 2	V5 Wk 4 ± 2d	V6 Wk 12 ± 1wk	V7 Wk 16³	V8 Wk 25 ± 2wk	V9 Wk 32 	V10 Wk 52 ± 2wk	LTFU
Information Letter and Phone Screen	Х												
ICF/ Assent/ HIPAA		Х											
Inclusion / Exclusion Criteria	Х	Х		X	Х								
Demographics	Х	X											
Medical / Medication History	Х	X		X	Х			X					
Concomitant Medications					Χ	Х	Χ	X	Χ	X	Х	X	
Adverse Events					Х	Х	Χ	X	Χ	X	X	X	X
Physical Exam		X			Х							Х	
Skin Exam 		Х	X	Х	Х	Х	Χ	X	Χ	X	Х	X	
Vital Signs		Х		Х	Х	Х	Χ	X	Χ	X	Х	Х	
Digital Imaging of Wounds		Х	Х	Х	Х	Х	Х	Х	Χ	Х	Х	Х	
Target Wound Selection				Х									
Investigator Assessment of Wound Healing							X	Х	Х	Х	Х	Х	
Bacterial Culture 				X	Х	Х	Χ	Х	Х	Х	Х	Х	
FCX-007 Administration					Х		Х						
Urine Pregnancy Test		Х		X									
Hematology & Chemistry		Х		X			Χ	Х	Χ	Х	Х	Х	
HIV, Hep B, Hep C Testing		Х											
RCL evaluation			X 				Χ	Х	Х	Х	Х	Х	X12
C7 Antibody Assay		Х					Χ	Х	Χ	Х	Х	Х	
Genetic Testing		Х											

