### 7.3.1 Visit 2 (Wound Selection/Run-In)

Visit 2 procedures may occur up to 2 days (±1 day) prior to the day of FCX-007 administration. The following procedures will be performed during Visit 2:

- Re-evaluation of inclusion/exclusion criteria
- Review of medical and medication history
- Skin Exam
- Vital signs: blood pressure, heart rate, respiratory rate, temperature
- Collection of blood (approximately 12.5 mL) for laboratory tests
  - Serum chemistry
  - Hematology
- Collection of urine for pregnancy test, if applicable
- Bacterial culturing of target wounds
- Final target wound selections of up to 3 pairs from the selected potential target wounds (See Section **9.1** for details)
- Label the selected target wound pairs as T1A and T1B for the 1st pair, T2A and T2B for the 2nd pair, and T3A and T3B for the 3rd pair.
- Digital imaging of wounds.

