### 7.3.4 Visit 5 (Week 4)

The visit window for the Week 4 visit is ±2 days. The following procedures will be performed during this visit:

- Assessment of adverse events
- Assessment of concomitant medications
- Skin exam
- Vital signs: blood pressure, heart rate, respiratory rate, temperature
- Collection of blood (approximately 19 mL) for laboratory tests:
  - Serum chemistry
  - Hematology
  - Analysis for C7 antibodies
  - RCL analysis
- Digital imaging of wounds
- Investigator Assessment of Wound Healing.
- Bacterial culturing of target wounds (may be done if clinical evaluation is indicative of infection).
- Skin biopsies will be collected for IEM, genomic DNA/mRNA and/or IF/DIF evaluation at the site of Investigational Product/placebo administration as outlined in **Table 2**. Biopsy location markings must be imaged prior to collection.
- Skin biopsies will be collected from intact skin administration sites for IEM, genomic DNA/mRNA and/or IF/DIF evaluation as outlined in **Table 2**.
- Surgical marking around the target wounds and on the intact skin
- Tattoos will be placed on non-blistered skin near the target wounds for the purpose of calibrating the post-dose imaging.
- Tattoos will also be placed next to the intact skin injection sites for the purpose of precisely locating the biopsy sites at follow-up visits.
- FCX-007 administration to target wounds
- FCX-007 administration to the intact skin.
- Post-dose digital imaging
- Post-dose assessment of concomitant medications and adverse events

CONFIDENTIAL Page 33 of 75

Final Version 8.0, 29 Oct 2019

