### 7.3.5 Visit 6 (Week 12)

The visit window for Week 12 is ±1 week. The following procedures will be performed during these visits:

- Re-evaluation of inclusion/exclusion criteria
- Review of medical history
- Assessment of adverse events
- Assessment of concomitant medications
- Physical and Skin exam
- Vital signs: blood pressure, heart rate, respiratory rate, temperature
- Collection of blood (approximately 19 mL) for laboratory tests:
  - Serum chemistry
  - Hematology
  - Analysis for C7 antibodies
  - RCL analysis
- Digital imaging of wounds
- Investigator Assessment of Wound Healing.
- Bacterial culturing of target wounds (may be done if clinical evaluation is indicative of infection).
- Skin biopsies will be collected for IEM, genomic DNA/mRNA and/or IF/DIF evaluation at the site of Investigational Product/placebo administration as outlined in **Table 2**. Biopsy location markings must be imaged prior to collection.
- Skin biopsies will be collected from intact skin administration sites for IEM, genomic DNA/mRNA and/or IF/DIF evaluation as outlined in **Table 2**.

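### No pregnancy test is scheduled before the second FCX-007 dose at Week 4, which falls 27 to 33 days after the last required test

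*Combined protocol and SAP*

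**What the plan says.** Section 4.2, exclusion no. 10, keeps out "Women who are pregnant or breast-feeding". Section 5.3, item 3, lists as grounds for withdrawal "Occurrence of unmanageable adverse events, or pregnancy".

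Section 11.6.2 sets the testing schedule: "A urine pregnancy test will be performed at the Visit 1 and Visit 2 for women of childbearing potential". The "Urine Pregnancy Test" row of Table 2 has two marks, under Visit 1 and Visit 2. The visit lists agree: urine collection for this purpose is in 7.1.3 (Screening) and 7.3.1 (Visit 2), and in no later list.

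FCX-007 is given twice, on Day 0 (Visit 3) and at Week 4 (Visit 5), according to the synopsis and sections 3.1 and 9.4.3. On supply, section 6.2.1.1 says: "Up to thirty (30) vials of FCX-007 will be provided per subject; 15 vials for Day 0, and 15 vials for week 4".

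The Visit 5 list (7.3.4) contains adverse events, concomitant medications, skin exam, vital signs, blood for chemistry, hematology, C7 antibodies and RCL, imaging, biopsies and administration. It has no pregnancy test and no re-check of eligibility. The list for Visit 6 (7.3.5) does have an eligibility re-check, but that visit comes after the second dose and also has no pregnancy test.

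**The concern.** The plan sets its own standard for the first dose. A woman is tested at screening and tested again within days of injection, because manufacturing puts about four months between the two. The second dose has the same maximum volume as the first but no test of its own, and the documents give no reason for the difference.

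A woman who conceives after Visit 2 may not know it by Week 4. No required step at Visit 5 would detect this before she is injected. Safety is the primary objective, the protocol describes the product as having no previous human use, and congenital abnormality is one of its criteria for a serious adverse event (13.1.2). What is at stake is avoidable exposure in pregnancy, not the validity of an analysis.

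**Working it through.** The protocol states no interval for this point, so there is no planned figure to reproduce. The intervals follow from the visit windows, with Day 0 as the first dose.

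**Inputs**

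- Visit 2 (7.3.1): "Visit 2 procedures may occur up to 2 days (±1 day) prior to the day of FCX-007 administration". Read as Day -2 ±1, this is Day -3 to Day -1.
- Visit 5 (7.3.4): "The visit window for the Week 4 visit is ±2 days". Week 4 is Day 28, so the range is Day 26 to Day 30.
- Visit 6 (7.3.5): "The visit window for Week 12 is ±1 week". Week 12 is Day 84, so the range is Day 77 to Day 91.
- Vials (6.2.1.1): 15 of up to 30 are for Week 4.

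**Intervals (later day minus earlier day)**

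| Interval | Shortest | Nominal | Longest |
|---|---|---|---|
| Last test to first dose | 0 - (-1) = 1 day | 0 - (-2) = 2 days | 0 - (-3) = 3 days |
| Last test to second dose | 26 - (-1) = 27 days | 28 - (-2) = 30 days | 30 - (-3) = 33 days |
| Second dose to the Visit 6 eligibility re-check | 77 - 30 = 47 days | 84 - 28 = 56 days | 91 - 26 = 65 days |

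**Sensitivity to the reading of Visit 2.** If the wording lets Visit 2 take place on Day 0 itself, the first row becomes 0 to 3 days and the second becomes 26 to 33 days (26 - 0 = 26).

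**Share of product.** 15/30 = 50% of the maximum planned vials are given without a preceding test.

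**Could another required step close the gap?**

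- Visit 5 list (7.3.4): no test, no eligibility re-check and no medical history review. Section 11.2 places history updates at Visits 2 and 3.
- Adverse event questioning (13.1.1): deliberately non-leading questions about health changes. They could bring out a known pregnancy but not an unrecognised one.
- Unscheduled procedures (7.4): at the investigator's discretion. A pregnancy test is not among the examples, and nothing is required.
- Visit 6 (7.3.5): too late for the second dose, and no pregnancy test. The inclusion/exclusion row of Table 2 has no mark at Visit 6 either, so even this re-check appears only in the visit list.

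None of these is a required check of pregnancy status before the second dose.

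**The case against.** The strongest reply is that the protocol does not strictly forbid dosing a pregnant subject at Week 4. Exclusion no. 10 governs entry, and section 5.3 is permissive: the investigator or sponsor may withdraw a subject, and pregnancy is one of the listed grounds. This is right as a reading of the wording. The gap remains, because listing pregnancy as a reason to withdraw does little before re-dosing if no one is required to look for it.

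The supporting figures also deserve caution. The 47 to 65 days end at a re-check that Table 2 does not show and that contains no pregnancy test, so they do not measure when a pregnancy would be found. The 50% is a share of a planned maximum and restates that one of two doses is uncovered. It is not a measure of risk. Neither figure carries the conclusion.

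Partial safeguards do exist: adverse event and medication review at Visit 5, and discretionary testing. They reduce the gap without closing it. The consent pages are not available, so any contraception or pregnancy-reporting instructions there cannot be checked. The documents at hand state no contraception requirement.

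Finally, few subjects are involved (up to 12, with one more possible in Phase II under section 3.3), and the documents give no fetal-risk data for this locally injected autologous product. That limits the expected harm. The remedy is correspondingly small.

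**Conclusion.** The concern holds. Section 11.6.2, Table 2 and the visit lists agree that pregnancy is tested only at Visits 1 and 2, and nothing else in the protocol requires a check before the Visit 5 dose. The last required test is then 27 to 33 days old (nominal 30), against 1 to 3 days for the first dose. These ranges assume that Visit 2 is Day -2 ±1 and that Week 4 is Day 28 ±2. Allowing Visit 2 on Day 0 lowers the two minimums to 26 and 0 days and changes nothing else.

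The point concerns only women of childbearing potential who conceive after Visit 2, or whose pregnancy was too early to show then. Their number cannot be derived. No estimate, test or sample size is affected. It should be corrected as a definite but small safety-procedure gap.

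The summary of changes suggests a possible origin: version 7.0 moved the second dose from Week 12 to Week 4, and the eligibility re-check still sits at Week 12. That is an inference, and the conclusion does not depend on it.

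**What to change.** Add a urine pregnancy test at Visit 5 for women of childbearing potential, with a negative result required before any FCX-007 injection. Three places need the change:

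- Table 2: a mark under Visit 5 in the pregnancy test row.
- Section 7.3.4: the test listed ahead of administration.
- Section 11.6.2: Visit 5 added, with the condition that the result must be negative before dosing.

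The interval from last test to second dose falls from 27–33 days to 0. A urine test can still miss a very recent conception, a limit that applies equally to the first dose.

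The cost is one non-invasive test per eligible woman, at an on-site visit that already takes blood and biopsies, plus the wording changes.
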